1. SYNOPSIS

Study Title	Characterising the stable and dynamic left atrial substrate in atrial fibrillation using high density contact and non-contact mapping			
Internal ref. no. / short title	CASDAF-HD			
Study Design	Prospective non-randomised mechanistic investigation			
Study Participants	Adults aged ≥18 with atrial fibrillation undergoing catheter ablation and 5 controls undergoing ablation of left sided accessory pathways			
Planned Sample Size	35 (30 patients with AF and 5 supravent	ricular tachycardia (SVT))		
Planned Study Period	2 years			
	Objectives	Outcome Measures		
Primary	To define the normal range of voltage amplitude identified using the Abbott EnSite Advisor HD grid (SE) catheter and HD wave solution and response to pacing cycle lengths using a control group with normal left atria	Mean and distribution of left atrial voltage amplitude across the whole chamber and by segments with lower limit of normal defined as the upper 95% value within the segment with the lowest mean amplitude at long pacing cycle length		
Secondary	To characterise the left atrial electrophysiological substrate using electroanatomical voltage and activation mapping using the Abbott EnSite Advisor HD grid (SE) catheter during pacing using a basic cycle length and a single closely coupled extra-stimulus in a cohort of patients undergoing catheter ablation for atrial fibrillation.	A change in electrogram morphology from normal to abnormal (defined as ≥3 deflections lasting ≥50ms) between long and short pacing cycle length in regions of low (<0.5mV), intermediate (0.5-lower limit of normal defined from control group) and normal (defined from control group results) voltage amplitude.		
	Difference in single vector conduction velocity at long and short cycle lengths in regions or low, intermediate and normal voltage. In a subgroup of 20 patients: To compare electroanatomic voltage mapping (EAVM) performed with a bipolar contact force guided ablation catheter to the Abbott HD grid using orthogonal wave analysis in sinus rhythm. In a subgroup of 10 patients: Difference in single vector conduction velocity at long and short cycle lengths in regions or low, intermediate and normal voltage amplitude by each method in sinus rhythm 2. Surface area and proportion points of scar (<0.05mV), low voltage (0.05-0.4mV), intermed voltage and normal voltage (voltage and normal voltage (voltage cut-offs defined from control group). Correlate electrogram amplitude and morphology with regions or low, intermediate and normal voltage area.			
	Correlate findings of high density	and morphology with regions of		

contact mapping with AF propagation patterns using the AcQMap combined imaging and electrophysiological mapping system.	uniform, irregular, slow or rotational activation patterns during AF.
To evaluate the distribution of late gadolinium enhancement on cardiac MRI relative to conduction properties identified using the HD grid (as above)	Electrogram amplitude, morphology and conduction velocities at long and short cycle length in regions with and without late gadolinium enhancement on cardiac MRI
Correlate dynamic propagation patterns with distribution of atrial scar derived from cardiac MRI	Difference in distribution of late gadolinium enhancement in regions of predominant rotational and irregular activation during AF.
Evaluate the effect of ablation on left atrial scar derived from cardiac MRI	Difference in burden of late gadolinium enhancement on preand post procedure cardiac MRI.
In 5 control patients: Evaluate the effect of cycle length on electrogram morphology in normal subjects	A change in electrogram morphology from normal to abnormal (defined as ≥3 deflections lasting ≥50ms), amplitude and duration between long and short pacing cycle length

2. ABBREVIATIONS

AF	Atrial fibrillation			
CI	Chief Investigator			
CRF	Case Report Form			
EAVM	Electroanatomic Voltage Mapping			
GCP	Good Clinical Practice			
GP	General Practitioner			
HRA	Health Research Authority			
ICF	Informed Consent Form			
LGE-MRI	Late Gadolinium Enhanced – Magnetic Resonance Imaging			
NHS	National Health Service			
NRES	National Research Ethics Service			
PI	Principal Investigator			
PIL	Participant/ Patient Information Leaflet			
R&D	NHS Trust R&D Department			
REC	Research Ethics Committee			
SOP	Standard Operating Procedure			
30P	Standard Sperding Frocedure			

3. BACKGROUND AND RATIONALE

Atrial fibrillation is a common condition resulting in significant morbidity and mortality. Catheter ablation based around a strategy of pulmonary vein isolation is increasingly used to maintain sinus rhythm.(1) However, particularly in patients with persistent atrial fibrillation, efficacy is limited with single-procedure success rates of <50%.(2-5) Although a number of techniques targeting non-pulmonary vein mechanisms have been explored, none has demonstrated superior efficacy in randomised controlled trials.(5) This is in large part due to a lack of understanding of AF mechanisms or subgroups of AF phenotypes and the contribution of identified conduction patterns to arrhythmia maintenance and propagation.

Assessment of atrial substrate is often performed through electroanatomical voltage mapping (EAVM) using multipolar or bipolar catheters. Regions of low voltage amplitude, used as a surrogate for fibrosis, predict worse outcomes following catheter ablation.(6-8) Prior studies have varied in the technology used to conduct EAVM and how low voltage areas are defined. They have largely focused on regions with bipolar amplitude <0.5mV with normal being defined as >1.1 or 1.3mV.(9, 10) The significance of regions with amplitude between these values (intermediate voltage) is poorly understood but there is some evidence that highly fractionated electrograms are seen in these areas(9, 10) which correlate with patchy enhancement rather than dense fibrosis on late gadolinium enhanced cardiac MRI (LGE-MRI). The presence of intermediate and low voltage areas is associated with AF recurrence following pulmonary vein isolation (PVI).(11, 12) Interestingly, a significant proportion of patients undergoing catheter ablation for persistent AF do not demonstrate regions of low voltage implying that it is not purely these regions that are important for AF maintenance.(7, 13) There also appears to be fairly poor correlation between AF duration and the presence of fibrosis, with some patients with longstanding AF demonstrating scar-free atria, whilst some with only brief episodes have highly scarred atria.(13, 14)

EAVM may significantly underestimate fibrosis when compared with MRI. One MRI study found >20% atrial fibrosis in 51% of patients and a second study found >10% fibrosis in 81%.(14, 15) Rolf's study assessing ablation of low voltage areas found these to be present in only 26% of patients.(7) This suggests that current strategies of EAVM fail to detect a significant proportion of fibrosis seen in MRI. This may be the result of regions of patchy fibrosis with relatively preserved voltage amplitude but abnormal conduction properties, important for AF propagation.

Studies have shown an increase in total atrial conduction time with increasing duration of AF and a corresponding slowing in conduction velocity.(10) Conduction velocities are significantly reduced in low voltage areas (<0.5mV) but are less thoroughly studied in regions of intermediate voltage.(16) Furthermore, the majority of this work has been undertaken in sinus rhythm. Conduction velocity and refractoriness are significantly affected by the interval between successive beats. Ectopic (premature) beats, usually originating in the pulmonary veins, commonly trigger AF. Therefore, although resting atrial conduction properties (and electrogram morphology) may appear normal, response to closely coupled ectopic activation could be impaired and contribute to the initiation and maintenance of fibrillation.

EAVM during AF is influenced by the effect of wavefront directionality on bipolar electrogram amplitude. The novel Abbott EnSite Advisor HD grid (SE) catheter uses orthogonal bipoles to reduce the

effect of wavefront direction (HD wave solution) and is therefore designed to facilitate more accurate substrate assessment compared to conventional bipolar mapping catheters. Appropriate voltage amplitude values representing the cut-off between normal and abnormal will vary with the catheter used (the result of electrode size and spacing) and has not been clearly defined with this technology.

The HD grid catheter is still a traditional "point by point" mapping system whereby small areas of the atrium are examined in sequence. Non-contact dipole density mapping facilitated by the AcQMap system from Acutus Medical allows real-time visualisation of whole chamber activation during AF and reveals complex propagation patterns. These patterns are highly variable between patients and their detailed analysis may identify important patterns related to the underlying electrophysiological substrate that may further our understanding of AF mechanisms and help guide effective ablation strategies.

This study therefore aims to conduct detailed EAVM using the Abbott HD grid catheter in 5 control patients undergoing ablation of left sided accessory pathways who are thought to have normal atria in order to define normal voltage amplitude and the response to changing activation rate. Detailed EAVM will then be performed in patients undergoing catheter ablation for AF in order to evaluate atrial properties at both long and short pacing cycle lengths. In 2 separate subgroups, the orthogonal HD grid mapping will be compared to either AcQMap propagation patterns or to a conventional bipolar ablation catheter with contact force. It is hypothesised that regions of intermediate voltage will demonstrate exaggerated slowing in conduction velocity and broadening of electrograms with shortening cycle length compared to regions of preserved amplitude, which will correlate with regions of slow and irregular propagation patterns during atrial fibrillation and late gadolinium enhancement on cardiac MRI. Furthermore, EAVM using the HD grid catheter will reveal higher mean electrogram amplitude compared to bipolar mapping with a lower surface area identified as low voltage (<0.5mV). The improved mapping resolution provided by the HD wave solution and HD grid catheter alongside use of varying activation times will facilitate greater understanding of the variable and patient specific AF substrate involved in AF maintenance. It is anticipated that combining this with non-invasive assessment of fibrosis distribution through cardiac MRI and AF propagation patterns visualised by panoramic mapping will provide pilot data with the potential to identify sub-groups of AF phenotypes. This data can then be applied to larger multi-centre studies of substrate mapping to better characterise the arrhythmic substrate and develop patient specific ablation strategies.

4. OBJECTIVES AND OUTCOME MEASURES

Objectives	Outcome Measures	Timepoint(s) of evaluation of this outcome measure (if applicable)
Primary To define the normal range of voltage amplitude identified using the Abbott EnSite Advisor HD grid (SE) catheter and HD wave solution and response to pacing cycle lengths using a control group with normal	Mean and distribution of left atrial voltage amplitude across the whole chamber and by segments with lower limit of normal defined as the upper 95% value within the segment with the lowest mean amplitude at long pacing cycle length	During ablation procedure

left atria		
Secondary: To characterise the left atrial electrophysiological substrate using electroanatomical voltage and activation mapping using the Abbott EnSite Advisor HD grid (SE) catheter during pacing using a basic cycle length and a single closely coupled extra-stimulus in a cohort of patients undergoing catheter ablation for atrial fibrillation.	A change in electrogram morphology from normal to abnormal (defined as ≥3 deflections lasting ≥50ms) between long and short pacing cycle length in regions of low (<0.5mV), intermediate (0.5-lower limit of normal defined from control group) and normal (defined from control group results) voltage amplitude.	During ablation procedure
	Difference in single vector conduction velocity at long and short cycle lengths in regions of low, intermediate and normal voltage.	During ablation procedure
In a subgroup of 20 patients: To compare electroanatomic voltage mapping (EAVM) performed with a bipolar contact force guided ablation catheter to the Abbott HD grid using orthogonal wave analysis in sinus rhythm.	1. Difference in voltage amplitude by each method in sinus rhythm 2. Surface area and proportion of points of scar (<0.05mV), low voltage (0.05-0.4mV), intermediate voltage and normal voltage (voltage cut-offs defined from control group).	During ablation procedure
In a subgroup of 10 patients: Correlate findings of high density contact mapping with AF propagation patterns using the AcQMap combined imaging and electrophysiological mapping system.	Correlate electrogram amplitude and morphology with regions of uniform, irregular, slow or rotational activation patterns during AF.	During ablation procedure
To evaluate the distribution of late gadolinium enhancement on cardiac MRI relative to conduction properties identified using the HD grid (as above)	Electrogram amplitude, morphology and conduction velocities at long and short cycle length in regions with and without late gadolinium enhancement on cardiac MRI	During ablation procedure
Correlate dynamic propagation patterns with distribution of atrial scar derived from cardiac MRI	Difference in distribution of late gadolinium enhancement in regions of predominant rotational and irregular activation during AF	N/A

Evaluate the effect of ablation on left atrial scar derived from cardiac MRI	Difference in burden of late gadolinium enhancement on pre-and post procedure cardiac MRI.	3-6 months post procedure
In 5 control patients: Evaluate the effect of cycle length on electrogram morphology in normal subjects	A change in electrogram morphology from normal to abnormal (defined as ≥3 deflections lasting ≥50ms), amplitude and duration between long and short pacing cycle length	During ablation procedure

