9.2. The Number of Participants

The total number of participants will be 35; 30 with AF and 5 controls. Previous studies have revealed the presence of low voltage areas (<0.5mV) in approximately 35% of patients with persistent AF undergoing catheter ablation,(7) and in the one previous prospective study of patients without low voltage areas, intermediate amplitude regions were observed in 43%.(9) Our hypothesis is that conduction properties, and thus electrogram morphology will become abnormal at shorter cycle length. A sample of 35 is consistent with previous mechanistic exploratory studies and should include enough patients with regions of voltage amplitude <1.1mV according to prior results outlined above and allow comparisons between each cycle length. As this is an exploratory study we are not evaluating a specific intervention, formal power calculations have limited usefulness.

The control group will consist of 5 patients with presumed normal atria. Although this is a small number, a high number of points will be collected to allow good distribution of results. By analysing the combined total electrogram recordings and excluding patients with any risk factors for abnormal atrial substrate then this sample should provide adequate estimation of normal values.

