9.3. Analysis of Outcome Measures

Control group:

All electrogram samples will be analysed at baseline (long) cycle length and classified as normal or abnormal (see above definitions in section 4). The same sampling points will then be analysed at short cycle length and classified in the same way. The proportion of electrograms changing from normal to abnormal will be recorded as will the change in electrogram amplitude and duration.

The whole chamber mean, median and distribution of voltage amplitude at long cycle length will be analysed. This will also be done for each atrial segment. The segment with the lowest mean amplitude will be identified and the cut-off for the value representing the upper 95% of recordings in that segment calculated. This will be used as the value representing the lower limit of normal for subsequent study analyses.

All participants:

All electrogram samples will be analysed at baseline (long) cycle length and classified as normal or abnormal (see above definitions in section 4). The same sampling points will then be analysed at short cycle length and classified in the same way. The proportion of electrograms classified as normal and abnormal at each cycle length will be calculated for the full sample set and according to baseline electrogram amplitude (<0.5mV, 0.5-lower limit of normal, and >lower limit of normal)(lower limit of normal defined above from analysis of the control group).

For each participant, conduction velocities will be analysed in regions of different baseline electrogram amplitude at both long and short cycle length. This will be done using the Turbomap feature in Precision to create an activation map (specified as measuring on maximum negative dV/dt). Conduction velocity will be calculated as a mean of 5 measurements using the difference in activation times between 2 points in a straight line at set distance through the region of least isochronal crowding. This will be done in regions of low, intermediate and preserved voltage at long and short cycle length.

The outcome measures will be assessed in all patients in whom the study procedure was performed.

Voltage mapping subgroup:

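### The 20-patient catheter comparison defines low voltage as 0.05-0.4 mV, but its own hypothesis, the main secondary outcome and the section 9.3 amplitude brackets use <0.5 mV

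*Combined protocol and SAP*

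**What the plan says.** **The catheter-comparison outcome.** In the section 4 table, the second outcome for the 20-patient subgroup is the surface area and proportion of points in four classes: scar below 0.05 mV, then "low voltage (0.05-0.4mV), intermediate voltage and normal voltage (voltage cut-offs defined from control group". The synopsis (section 1) gives the same figures: "scar (<0.05mV), low voltage (0.05-0.4mV".

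**The hypothesis it serves.** Section 3 predicts that the HD grid will give a higher mean amplitude than bipolar mapping, "with a lower surface area identified as low voltage (<0.5mV".

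**Other class definitions in the study.** The main secondary outcome, in the same section 4 table, looks for morphology change "in regions of low (<0.5mV), intermediate (0.5-lower limit of normal defined from control group". Section 9.3, under *All participants*, tabulates electrograms "according to baseline electrogram amplitude (<0.5mV, 0.5-lower limit of normal, and >lower limit of normal".

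**Prior evidence.** Earlier findings are quoted at 0.5 mV too: "Conduction velocities are significantly reduced in low voltage areas (<0.5mV" (section 3) and "Previous studies have revealed the presence of low voltage areas (<0.5mV) in approximately 35% of patients with persistent AF" (section 9.2).

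**The analysis text for this subgroup.** Section 9.3, *Voltage mapping subgroup*, describes mean amplitudes by chamber and segment and paired nearest-point differences. It gives no voltage classes and no analysis of area or proportion.

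**The concern.** The upper limit of low voltage differs between an outcome and the hypothesis it is meant to test, and between two outcomes in one table. The same HD-grid point in the same patient, at 0.45 mV for example, is low under the main secondary outcome. Under the catheter comparison it is either intermediate or in no class. No passage explains 0.4 mV.

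Two things are at stake. First, the low-voltage-area half of the catheter hypothesis is not measured at its own threshold. Second, an analyst who notices this later must choose between 0.4 and 0.5 mV with the data in hand, in a comparison that section 5 describes as non-blinded.

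A smaller, separate point concerns the boundary between intermediate and normal. It comes from the control group, who are mapped only with the HD grid (section 7.6). Section 3 says that such cut-offs depend on the catheter. The plan does not say why the HD-grid limit should apply to the ablation-catheter map.

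**Working it through.** **1. The definitions side by side**

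| Place | Low voltage | Intermediate starts at |
|---|---|---|
| Sections 1 and 4, 20-patient outcome | 0.05-0.4 mV (scar <0.05 mV) | no figure given |
| Section 3, catheter hypothesis | <0.5 mV | not stated |
| Sections 1 and 4, main secondary outcome | <0.5 mV | 0.5 mV |
| Section 9.3, *All participants* | <0.5 mV | 0.5 mV |
| Section 9.3, *Voltage mapping subgroup* | none given | none given |

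**2. Can they be reconciled?**

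- *Extraction error.* Unlikely: 0.05-0.4 appears in two separate tables.
- *Scar split off from low.* Scar plus low covers 0 to 0.4 mV, still not 0 to 0.5 mV. The split itself is only a subdivision and is no conflict.
- *Cut-offs taken from the control group.* Section 9.3 derives a single value from controls, the lower limit of normal. That does not set the low/intermediate boundary, and 0.4 mV is already a fixed number.
- *Analysis text for the subgroup.* It contains no classes, so it cannot decide.

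The conflict therefore stands without any arithmetic.

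**3. How large could it be?** The documents give no amplitude distribution, so everything in this step is assumed: log-normal point amplitudes, median *m* from 0.8 to 3.0 mV (steps of 0.1) and log-SD *s* from 0.6 to 1.0 (steps of 0.05). The share of points below *x* is F(x) = Φ(ln(x/m)/s).

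Disputed band, F(0.5) − F(0.4):

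- Largest, at m = 0.8, s = 0.6: 0.2167 − 0.1240 = 0.0927, which is 300 × 0.0927 ≈ 28 points of a 300-point map.
- Smallest, at m = 3.0, s = 0.6: 0.0014 − 0.0004 = 0.0010, or about 0.3 of 300 points.

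Band as a share of all points below 0.5 mV:

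- Lowest, at m = 0.8, s = 1.0: 0.0751/0.3192 = 0.235.
- Highest, at m = 3.0, s = 0.6: 0.722.

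**4. Effect on the between-catheter contrast.** Assume also that the ablation-catheter median is *r* × *m*, with r = 0.9, 0.8 or 0.7 and the same *s*. The contrast is the ablation-catheter proportion minus the HD-grid proportion.

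| Case | Contrast at <0.5 mV | Contrast at 0.05-0.4 mV | Ratio |
|---|---|---|---|
| m 0.8, s 0.6, r 0.7 (largest contrast) | 0.4251 − 0.2167 = 0.208 | 0.2874 − 0.1240 = 0.163 | 0.78 |
| m 3.0, s 0.6, r 0.9 (smallest contrast and ratio) | 0.0011 | 0.0003 | 0.318 |
| m 0.8, s 0.95, r 0.7 (largest ratio) | 0.142 | 0.125 | 0.880 |

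Over the whole grid the ratio runs from 0.318 to 0.880 and the sign never changes. Scar contributes little: F(0.05) is at most 0.0028 for the HD grid and 0.0078 for the ablation catheter. These are proportions of points; surface area was not modelled.

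**5. Patients likely to carry low-voltage areas.** Section 3 says an earlier study "found these to be present in only 26% of patients"; section 9.2 gives 35% for persistent AF. If either rate applied here, 20 × 0.26 = 5.2 to 20 × 0.35 = 7.0 patients would contribute. The subgroup may include paroxysmal AF, so this is only a guide.

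**The case against.** The mismatch itself is not in dispute; the case against is that it is small and that its reach can be overstated.

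- *Some uses of <0.5 mV are citations.* Section 9.2 and part of section 3 report earlier studies and do not define classes for this one. That is correct. The binding conflicts are with the hypothesis, the main secondary outcome and the *All participants* brackets, and those are enough.
- *A <0.5 mV analysis is not wholly unplanned.* The hypothesis states it in advance, and the *All participants* brackets already classify these patients' HD-grid points at 0.5 mV. This stands in part. Still missing are the same class on the ablation-catheter map and the area on either map, while the listed outcome points to 0.4 mV.
- *The size is driven by assumption.* True. The 72% share and the 32% ratio occur where only about 0.14% of points lie below 0.5 mV, or where the whole contrast is about 0.1 percentage point. Where the contrast is at least 5 points, the outcome as written keeps about half of it or more.
- *One common threshold is a natural way to compare two catheters.* Fair. The control-group point therefore calls for a stated rationale and does not show an error.
- *0.4 mV may be deliberate.* Possible, but nothing in the documents says so. If it is, it needs a reason and the other definitions need a bridge to it.

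**Conclusion.** The concern holds. The plan sets two upper limits for low voltage, and the one attached to the catheter comparison is not the one in the hypothesis it tests. Nothing in the current text resolves this.

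The consequence is limited. One of two measures in one exploratory subgroup objective is affected. Mean amplitudes, paired point differences, the primary outcome and the sample size are not. Point amplitudes are kept, so the <0.5 mV result can be recovered.

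The numerical size cannot be fixed from the documents. Under the stated log-normal and catheter-scale assumptions it ranges from negligible to about 9% of all points, with part of the hypothesised contrast lost in every scenario and no change of direction. The inconsistency does not depend on those assumptions; only its size does. It should be corrected before the subgroup is analysed.

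**What to change.** - In sections 1, 4 and 9.3, set the low/intermediate boundary at 0.5 mV for the catheter comparison, and report scar (<0.05 mV) as a sub-class of <0.5 mV. If 0.4 mV was intended, give the reason and keep <0.5 mV as the class that tests the hypothesis.
- In the section 9.3 *Voltage mapping subgroup* text, add the total surface area and proportion of points below 0.5 mV for both catheters.
- State that the HD-grid lower limit of normal is applied to both catheters as a common descriptive threshold. State too that area differences at any shared threshold, 0.5 mV included, partly reflect the catheters' different amplitude scales.

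The cost is protocol wording only, with no extra mapping or data. The one drawback is a slightly more cautious reading of the intermediate and normal areas.
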